7.9.4 Ancillary Objectives

The ancillary objectives will further characterize the performance of the DiamondTemp Ablation System. All ancillary endpoints will be analyzed descriptively. Analysis of all ancillary objectives will use available data with no imputations for missing data, and the percentage of missing data will be displayed for each analysis.

7.9.4.1 Ancillary Objective #1

Objective

To characterize procedural characteristics.

Endpoint Definition and Derivation

The following procedure characteristics will be summarized for all index ablation procedures:

- Total procedure time (minutes), defined as time of investigational catheter insertion into the vasculature to time of last ablation catheter removal.
- Total treatment device time (minutes), defined as time of delivery of first RF ablation with the investigational catheter to removal of the catheter.
- Mean cumulative RF Time (minutes).
- Mean duration of RF ablations (seconds).
- Total fluid infused through the investigational catheter (mL).
- Total fluoroscopy time (minutes).

Analysis Methods

This ancillary endpoint will be analyzed using descriptive statistics.

Determination of Subjects/Data for Analysis

[figure not shown]
All subjects in the mITT population will be included in the analysis. The analysis will be based on index ablation procedures only.

7.9.4.2 Ancillary Objective #2

Objective

To characterize the number of re-hospitalizations due to Atrial Fibrillation recurrence during the effectiveness evaluation period.

Revision 1 Page 17 of 18

Endpoint Definition and Derivation

The number of re-hospitalizations due to Atrial Fibrillation recurrence during the effectiveness evaluation period will be calculated for each subject.

Analysis Methods

This ancillary endpoint will be analyzed using descriptive statistics.

Determination of Subjects/Data for Analysis

All subjects in the mITT population will be included in the analysis.

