6. Determination of Sample Size

For the primary safety endpoint, a sample size of 269 achieves 81% power to detect a difference of at least -4.5% using an Objective Performance Criterion (OPC) of 11.5% and a one-sided target level of significance of 0.025. Reference Section 7.9.1 for relevant statistical hypotheses.

Similarly, for the primary effectiveness endpoint, a sample size of 274 yields 86% power to detect a difference of 9% using an OPC of 40% and a one-sided target level of significance of 0.025. Reference Section 7.9.2 for relevant statistical hypotheses.

Assuming a drop-out rate of 12%, as well as accounting for eligibility/screen failures, the enrollment goal of up to 376 subjects should be sufficient.

7. Statistical Methods

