7.9.2 Primary Effectiveness Objective

Primary Effectiveness Objective

To demonstrate that the primary effectiveness rate associated with the DiamondTemp ablation system is higher than the pre-specified Objective Performance Criterion (OPC).

Hypothesis

Revision 1

Page 11 of 18

 H_0 : $P \leq P_0$

 $H_1: P > P_0$

where $P_0 = 40\%$ (Effectiveness OPC), and higher effectiveness rates are better.

Endpoint Definition and Derivation

The primary effectiveness endpoint is defined as freedom from documented Atrial Fibrillation (AF), Atrial Flutter* (AFL) and Atrial Tachycardia (AT) episodes following the blanking period (3-month followup post-ablation procedure) through the end of the effectiveness evaluation period (12-month followup post-ablation procedure).

An effectiveness failure is defined by any of the following events:

- Inability to electrically isolate all accessible targeted pulmonary veins during the ablation procedure.
- Documented episodes of AF, AFL or AT lasting ≥ 30 seconds in duration as evidenced by electrocardiographic data during the effectiveness evaluation period.
- DC cardioversion for AF, AFL or AT during the effectiveness evaluation period.
- A repeat ablation procedure to treat AF, AFL or AT during the effectiveness evaluation period.
- Use of a new or previously failed anti-arrhythmic drug (AAD) at a dose greater than the highest ineffective dose for AF during the effectiveness evaluation period.
- Use of a non-study device for ablation of any AF targets during the index or repeat ablation procedure during the blanking period.
- More than one (1) repeat ablation procedure during the blanking period.

The blanking period for a subject starts on the date of the index ablation procedure (day 0) and ends on day 90 post index ablation.

The effectiveness evaluation period for a subject starts on day 91 post index ablation and ends on the study exit date or day 410 post index ablation (i.e., close of the 12-month visit window), whichever is earlier.

If a primary effectiveness failure event occurs post day 365 and within the effectiveness evaluation period, the date of the event will be set to day 365 so that these events will be accounted for in the 12month Kaplan-Meier estimate of the primary effectiveness endpoint.

Performance Requirements

The null hypothesis will be rejected if the one-sided 97.5% lower confidence bound of the primary effectiveness rate is greater than 40%.

[figure not shown]

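### Ancillary Objective #2 summarizes AF re-hospitalizations as a raw count per subject over unequal follow-up, with no exposure denominator and no rule for exits before day 91

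*SAP*

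**What the plan says.** SAP 7.9.4.2 defines the endpoint in one sentence: "The number of re-hospitalizations due to Atrial Fibrillation recurrence during the effectiveness evaluation period will be calculated for each subject". On method it says "This ancillary endpoint will be analyzed using descriptive statistics", and on the analysis set "All subjects in the mITT population will be included in the analysis". Protocol 14.6.2 has the same definition, method and population. Neither mentions a rate, a person-time denominator or incomplete follow-up.

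The length of the period is set in SAP 7.9.2: "The effectiveness evaluation period for a subject starts on day 91 post index ablation and ends on the study exit date or day 410", whichever comes first. The 12-month visit window is 365 ± 45 days (Protocol 10.3, Table 9), that is, day 320 to day 410. Protocol 10.9 allows no further data collection once a subject has withdrawn.

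The general rule for ancillary objectives is in SAP 7.9.4: "Analysis of all ancillary objectives will use available data with no imputations for missing data, and the percentage of missing data will be displayed".

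**The concern.** A count of events is interpretable only with the time over which events could be seen. Here that time differs between subjects by the SAP's own definition, and the summary ignores it. A subject who exits event-free at day 150 has been observed for 60 days of the period but gives the same zero as a subject followed event-free to day 410. That zero is an available value, so the missing-data rule does not flag it.

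The SAP deals with this elsewhere. The primary analyses censor premature discontinuations at last contact (7.4) and move effectiveness failures after day 365 back to day 365 (7.9.2). Secondary Objectives 1, 2, 3, 5 and 6 use Kaplan-Meier. Secondary Objective 4 and Ancillary Objective #1 describe the procedure, and Secondary Objectives 7 and 8 are measured at visits. Among the secondary and ancillary objectives, this is the only one that accumulates events over follow-up with neither censoring nor a denominator.

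At stake is the meaning of the reported mean: two cohorts with the same admission rate could show different means because of dropout and visit scheduling. For exits before day 91, two programmers could also choose different denominators, and neither would contradict the SAP.

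**Working it through.** **Plan figures.** The documents give no expected value for this endpoint, so there is none to reproduce. The one planning figure used is the 12% dropout rate (SAP section 6). It is consistent with the sample size there: 274/(1 − 0.12) = 311.4, so 312, below the ceiling of 376.

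**Observation time (SAP 7.9.2, Protocol Table 9).**
- Completer seen at day 320: 320 − 90 = 230 days.
- Completer seen at day 365: 365 − 90 = 275 days.
- Completer seen at day 410: 410 − 90 = 320 days.
- Longest to shortest: 320/230 = 1.39.
- Dropout: 0 to 320 days.

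**Assumptions not in the documents.** The event rate is constant and unrelated to dropout. Dropout times are uniform over days 0 to 365. Completers leave at the 12-month visit. The day-91-to-410 definition applies here because SAP 7.9.4.2 uses the same term. The reference is the mean count with everyone followed from day 91 to day 365 (275 days). Under a constant rate, the expected raw mean divided by this reference equals the average observed days divided by 275.

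**Dropout effect, completers ending at day 365.** Let d = 0.12 and let f = 90/365 = 0.2466 be the share of dropouts who leave before day 91. The rest lose half the window on average.
- Subjects exiting before day 91: d × f = 0.12 × 0.2466 = 0.0296, about 3.0%.
- Dropouts' contribution: d × (1 − f) × 0.5 = 0.12 × 0.7534 × 0.5 = 0.0452.
- Early exits scored zero: 0.88 + 0.0452 = 0.925, a shortfall of 7.5%.
- Early exits treated as missing: 0.9252/(1 − 0.0296) = 0.953, a shortfall of 4.7%.

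**Adding visit timing.** Completers contribute 0.88 × (days/275).

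| Completers end at | Early exits scored zero | Early exits missing (divide by 0.9704) |
|---|---|---|
| Day 320 | 0.88 × 0.836 + 0.0452 = 0.78 | 0.7812/0.9704 = 0.81 |
| Day 365 | 0.88 × 1.000 + 0.0452 = 0.925 | 0.9252/0.9704 = 0.953 |
| Day 410 | 0.88 × 1.164 + 0.0452 = 1.07 | 1.0692/0.9704 = 1.10 |

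With early exits scored zero, the ratio is 1 when the average completer exit is day 90 + 275 × (1 − 0.0452)/0.88 = 388.

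**Sensitivity to dropout (completers ending at day 365, early exits scored zero).** If all dropouts leave uniformly over days 91 to 365, the ratio is 1 − d/2. If all leave before day 91, it is 1 − d.
- d = 5%: 0.975 to 0.95.
- d = 12%: 0.94 to 0.88.
- d = 20%: 0.90 to 0.80.

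**With a denominator.** Total events divided by total person-time has a ratio of 1.00 in every scenario above, because numerator and denominator shrink together under these assumptions.

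**The case against.** The best defence is that the plan already answers its own question. The objective is to characterize a number of re-hospitalizations, and a count with descriptive statistics does so. The trial has one arm. Regional and subgroup comparisons are specified only for the primary endpoints, and success rests on the two primary objectives. Attrition, follow-up compliance and reasons for discontinuation are reported (SAP 7.1.1, Protocol 14.2), so incomplete follow-up will be visible. All of this stands, and it limits the importance of the point. It does not make the mean count interpretable, because a disposition table does not tell the reader how much time the mean covers.

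A reader might infer from "All subjects in the mITT population will be included in the analysis" that early dropouts are entered as zeros. The documents do not say so. The same sentence is used for the AFEQT and NIH stroke scale changes, where an unmeasured subject cannot have a value, so it names the analysis set and sets no zero-fill rule. A subject who exits before day 91 has no evaluation period, and the no-imputation rule fits missing at least as well as zero. Events before exit are counted. What remains is that the rule is unstated for exits before day 91, and that the missing-data rule does not reach event-free exits after day 91.

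A further objection concerns capture: Protocol Table 8 has no re-hospitalization item, and Protocol 12.4 does not treat admissions for recurrent AF, AT or AFL as adverse events. That is a separate question. The planned count already needs admission dates to place events in the period, so a rate adds no new requirement on that side.

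**Conclusion.** The point holds as a minor gap in method. The endpoint is a raw count over observation times that run from 0 to 320 days, without a denominator and without a rule for exits before day 91.

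It is tempting to conclude that the count must understate the burden. The documents do not support that. A shortfall of about 5% to 7.5% is measured against a fixed window ending at day 365, with 12% uniform dropout and completers ending at day 365. The SAP's period extends to day 410, and late 12-month visits can offset or reverse the shortfall: with early exits scored zero, the ratio runs from 0.78 to 1.07. The supported conclusion is that the mean depends on dropout and visit timing, in a direction that cannot be fixed in advance.

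These sizes rest on a constant event rate, non-informative dropout and an assumed dropout pattern, none of which the documents give. The primary and secondary results are unaffected.

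**What to change.** In SAP 7.9.4.2, keep the raw count and add:

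- The total number of AF re-hospitalizations divided by total person-time from day 91 to exit or day 410, per subject-year. Give a 95% CI that allows for repeat admissions within a subject, for example by robust variance or a subject-level bootstrap; a simple Poisson interval could be too narrow.
- The distribution of evaluation-period follow-up time (number of subjects, median, quartiles, range).
- A rule that subjects with no follow-up after day 90 contribute no exposure and are excluded from the mean count, with their number shown.

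A person-time rate corrects for unequal exposure, but not for dropout that is itself related to AF recurrence, so the text should state that assumption.

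The cost is a little extra programming using exit dates and the admission dates that the planned count already needs. Under SAP 7.11 a CIP amendment is required only if a principal feature changes, which an added descriptive line for an ancillary objective would not ordinarily be.

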7.10 Safety Evaluation

Adverse event classifications and definitions are described in the Clinical Investigational Plan.

An overall summary of adverse events will be presented to include the number and percentage of subjects who report at least one adverse event, the total number of adverse events, the number of adverse events and the number and percentage of subjects who report adverse events by seriousness and relationship to the study treatment (i.e., study ablation procedure or device). For events adjudicated by the CEC, the CEC classifications will be used in the analysis; in cases where only the investigator classifies the event, the investigator's classification will be used.

The frequencies and percentages of adverse events will be presented by MedDRA system organ class (SOC) and preferred term (PT). The frequencies and percentages of AEs judged to be at least possibly related to study treatment will be presented by MedDRA SOC and PT. Similar tables will be presented for the subset of serious adverse events (SAEs).

Complete subject listings of all adverse events, all SAEs, and all AEs at least possibly related to study treatment will be provided. For each adverse event the following details will be specified: start and stop dates, event description, MedDRA SOC and PT, relationship to study ablation device, relationship to study ablation procedure, actions taken, outcome of the adverse event and seriousness (yes/no).

A summary table of all deaths will be compiled to summarize death classification and relationship to study treatment. A detailed listing of all deaths will also be provided.

A detailed listing of all reported device deficiencies will be provided.

7.11 Changes to Planned Analysis

This SAP has been developed prior to database lock to further describe the statistical methods and planned analyses of the study data to be included in the clinical study report. Any change to the data analysis methods described in the CIP will require a CIP amendment only if it changes a principal feature of the CIP. Any other change to the data analysis methods described in the CIP or SAP, and the justification for making the change, will be described in the clinical study report.

Validation Requirements 8.

All data analyses for the clinical study report (CSR) will be validated. Levels of validation required for the different elements of the CSR are specified in the table below.

Page 18 of 18

Form
Medtronic

Validation Level	Definition	Required for
Level I	A peer reviewer independently programs output and then compares the output with that generated by the original author of the program to be validated	All analyses in the CSR pertaining to the primary safety and primary effectiveness objectives of the study
Level II *	A peer reviewer reviews the program, and where appropriate, performs calculations or programming checks to verify the output	All other analyses in the CSR *

Revision 1

^{*}At a minimum, Level II validation will be performed.
